Aim 1: Conduct a feasibility and acceptability study of the RELAX approach in migraine and post-traumatic headache (PTH) patients who visit the NYU Department of Neurology General Practice and/or subspecialty groups or the NYU Concussion Center. We will recruit and randomize subjects (N=400) in the FGP Neurology Group including the MS Center and Headache Center and the NYU Concussion Center to receive the RELAX intervention or monitored usual care (MUC). Both groups will be asked to complete daily diaries, and data will also be collected on measures of recruitment, retention, adherence, and satisfaction with the PMR, the clinically important endpoint. With the PMR, we hypothesize that at least 70% of participants will be adherers (e.g., use RELAXaHEAD at least 4 days/week for 12 weeks). We will assess if the daily diary is acceptable by examining whether there is differential attrition with daily diary completion. We hypothesize no difference between the two groups for acceptability of the diary. We will define acceptability as an average score of ≥4 (0-5 Likert scale) on the 9-item acceptability questionnaire. The outcomes for Aim 1 are the feasibility/acceptability outcomes; number of days of diary entered, number of days of pmr, time spent/day on pmr (Please refer to Table 2)

Aim 2: Conduct within group analyses of the RELAX approach vs MUC.

In the migraine patient population, the primary outcome will be migraine quality of life and migraine disability measured by Migraine Quality of Life (MSQ) and the MIDAS. In the migraine-MS population, a primary outcome will also be MS pain related disability as measured by the MOS Pain Effects Scale (PES). ¹⁵ Secondary outcomes include headache frequency and intensity, stress levels, sleep and psychiatric screens (NIH PROMIS depression and anxiety screens). We hypothesize that at 3 months compared with baseline there will be trends in the RELAX arm towards decreased disability (as measured by the Migraine Disability Assessment Scale (MIDAS)) and improvements in MS pain related quality of life in the MS-migraine patient population.

In the PTH patient population, we will examine the secondary outcomes noted above.

Background

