Our initial sample size was justified based on the feasibility outcome of compliance with PMR among patients in the RELAX group. We anticipated an initial compliance rate of at least 75%. The planned sample size also provided adequate power for the primary exploratory outcome (\square MIDAS from baseline to 3 months) and the secondary outcome (number of headaches/30 days). Considering \square MIDAS as the primary outcome can reduce data skewedness and improve study power. Based on the study, the standard deviation (SD) of \square MIDAS ranges from 5 to 7. Using the conservative estimate of SD=7, group sample sizes of 30, with anticipated 25% dropout leading to approximately 23 patients per group, achieve 80% power to detect a clinically significant difference of 5.75 between the groups, assuming a significance level of 0.05 using a two-sided two-sample t-test.

Subsequently, based on later data, we found that only about half of the participants have full follow-through so the 90 (similar to the NIH request) is more adequate for this.

GenderofSubjects

Both genders will be included.

AgeofSubjects

18-80 (18 – 65 in urgent care)

Racialand Ethnic Origin No enrollment restrictions.

Inclusion Criteria [Box1] age 18-80;(18-65 in urgent care)

Meets migraine criteria based on International Classification of Headache Disorders (ICHD) 3 beta (based on questions in REDCap), Migraine Disability Assessment (MIDAS) score >5. 4+ headache days a month.

OR

Meets Chronic PTH criteria based on International Classification of Headache Disorders (ICHD) 3 beta (based on questions in REDCap) and had 4+ headache days a month, is 3-12 months post initial injury.

OR

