In addition, if any subject contacts us and want to withdraw from the study, we will ask them to complete the MSQv2 and MIDAS before they withdraw. Subjects who withdrew will be contacted via telephone or email at the end of the 6 months study period in order to verify their email address to be used to send the reimbursement gift card for their study participation. An IRB approved telephone voicemail and email script will be used. An attempt will be made to reach the subject via telephone and a voicemail will be left if unanswered. Following this, an email will be sent.

In addition, we will be conducting focus groups of patients who consented for the study to obtain additional feedback regarding the study procedures. Focus groups will range from 3-7 people with a goal of 5 participants per group. Participants will receive invitations to participate in the focus groups over telephone or over email. If they agree to do so, they will sign an informed consent form at the focus group meeting. Participants will be given a \$50 dollars for participating in the group. The focus group duration will be one hour.

Symptoms Diary

On the smartphone application platform developed by IRODY [end user agreement was already signed as part of prior study-see attached] (used by the NYUMC epilepsy group for ongoing IRB approved studies and in another IRB approved headache study), subjects will be trained to keep records of headache occurrence, side effects, compliance and medicine changes on their mobile device. If a subject fails to consistently record their data, they will receive a call from the RV at NYU to ensure compliance with data maintenance. Information prompted by the device will include:

- 1. Headaches (number, intensity, duration, time)
- 2. Abortive and preventive migraine drug treatment

- 3. Concomitant medications
- 4. Episodes of non-compliance
- 5. Changes made to migraine medication treatment plan, if any, and reasons for the change
- 6. Adverse effects, including severity, seriousness, unexpectedness as part of pharmacovigilance
- 7. Mood and anxiety and stress levels, sleep quality and duration
- 8. Healthcare utilization

The symptoms diary may be accessed via the mobile application only.

The study team will not share the symptoms diary information with the subject's treating physician. However, subjects can elect to share their data with their treating physician independently.

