The following questionnaires: PROMIS depression and anxiety screens, Insomnia Sleep Index (ISI) and the Perceived Stress Scale will be administered via REDCap.

In addition to the application, REDCap, a HIPAA Compliant research database system will be used. The study identifier and the PHI of the subjects will be stored in REDCap. In addition, we will use REDCap to send out the MIDAS to the subjects.

We will use the REDCap randomization feature to randomize our subjects.

DataAnalysis and DataMonitoring Analysis Plan

Table 2 describes the outcome measures that will be used. We considered the feasibility outcome measures recommended by Kraemer and colleagues for pilot studies.³¹ For this study, feasibility will be operationally defined as study recruitment, retention, and adherence measures for doing the PMR. Acceptability will be operationally defined as attrition, satisfaction, and willingness to participate in a similar intervention in the future. Satisfaction questions are as follows:

Responses will be 0-5 on the Likert Scale:

Daily Diary Satisfaction Questions

- 1. The app was easy to use
- 2. The information was easy to understand
- 3. The daily diary was relevant to me to help track my headaches
- 4. The app kept my interest and attention
- 5. I would be happy to use the app again

PMR Satisfaction Questions

- 1. The relaxation kept my interest and attention
- 2. The relaxation helped to improve my stress and low mood
- 3. The relaxation taught me skills that will help me handle future problems
- 4. I would be happy to do the relaxation again

Our primary outcome will be the change in the MSQv2 -a validated migraine quality of life measure (https://eprovide.mapi-trust.org/instruments/migraine-specific-quality-of-life-questionnaire). We will also use the Migraine Disability Assessment Scale (MIDAS), measures disability over the past 3 months. 32-35 MIDAS scores have been shown to have excellent test-retest reliability, high internal consistency, and high external validity using a variety of measures—including diary-based measures. 32,34 MIDAS scores are also positively associated with physician judgements about the severity of headache and the need for treatment. 33 In the MS- migraine patient population, we will also assess the MOS Pain Effects Scale (PES).

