Disability is a commonly used outcome in migraine trials evaluating outcomes of acute and preventative interventions, ^{36,37} because it is easy to understand and is meaningful to patients.

TABLE 2: OUTCOME MEASURES: DEFINITIONS AND SCALES

Aim 1: FEASIBILITY AND ACCEPTABILITY OUTCOMES

Feasibility: a) Proportion of patients who enrolled in the study/were recruited for the study, b) Percentage of patients who did PMR ≥4/7 days of the week, c) Number of days spent doing PMR ≥5 minutes/day as determined with the backend analytics in the RELAXaHEAD app, d) Minutes/day spent doing PMR, e) Reasons for non-adherence

Acceptability: a) Satisfaction using Likert scale questions on RELAXaHEAD usability, content, and functionality b) Willingness to repeat a similar treatment intervention in the future (Definitely No/Probably No/Unsure/Probably Yes/ Definitely Yes) c) Attrition

Aim 2: MIGRAINE QUALITY OF LIFE AND MIGRAINE DISABILITY OUTCOMES

Primary Outcome = Functionality: □□MIDAS: difference between scores of MIDAS ^{32,38} at 3 months and baseline. MOS Pain Effects Scale (PES).

Pain: 50% decrease in frequency and/or intensity of HAs (measured by electronic HA diary data).³⁹ Will control for adherence with PMR. (*Frequency*: # of HA days/30 days starting and ending at midnight; *Intensity*:0 (no HA), 1 (mild HA), 2 (moderate HA), 3 (severe HA) recommended by IHS.³⁹

Acute medications used*: As recommended by IHS:# of days/week treated with medications, # of drug administrations/week for medications. Medications included: NSAIDs, acetaminophen, caffeine, aspirin, triptans, barbiturates, opioids, antipsychotics.

Psychiatric Comorbidity, Stress Levels, and Sleep: PROMIS depression and anxiety screens, the Perceived Stress Scale, 42-44 and Sleep Duration and Quality using Likert Scale questions (How would you rate the quality of your sleep/How rested or refreshed did you feel when you woke-up for the day). 45

Adverse Events: *PMR*: Paradoxical anxiety, time burden/inconvenience, and any other adverse events experienced. Recorded in real time in the study diary.³⁹ As recommended by the IHS: Adverse events will be recorded as follows: Event Severity: Mild, Moderate, Severe; Event Seriousness: Serious, Non-Serious, Start and End Time.³⁹

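### Subjects who withdraw are not asked the satisfaction or willingness items, so the Aim 1 criterion of a mean of at least 4 is at risk of upward bias

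*Combined protocol and SAP*

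**What the plan says.** Aim 1, under Purpose of the Study, sets the pass mark: "We will define acceptability as an average score of ≥4 (0-5 Likert scale) on the 9-item acceptability questionnaire". The Analysis Plan lists the components more widely: "Acceptability will be operationally defined as attrition, satisfaction, and willingness to participate in a similar intervention in the future". It then gives five diary items and four PMR items, which together make the nine. Table 2 lists "Willingness to repeat a similar treatment intervention in the future" as a separate five-category item with no threshold, and lists attrition beside it.

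Methods & Procedures says what happens "if any subject contacts us and want to withdraw from the study": "we will ask them to complete the MSQv2 and MIDAS before they withdraw". It goes on: "Subjects who withdrew will be contacted via telephone or email at the end of the 6 months study period", and the stated purpose is "in order to verify their email address to be used to send the reimbursement gift card". No questionnaire is mentioned for that contact.

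The same section assigns MSQv2 and MIDAS to months 1, 2 and 3. It assigns the satisfaction and willingness items to no contact, and nothing says how a missing satisfaction score is handled. The rule in the sample-size text that counts dropouts as failures covers adherence only.

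On the amount of loss, the sample-size text assumes 25% dropout and then reports that "only about half of the participants have full follow-through".

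**The concern.** The plan foresees early leaving and specifies what to collect when it happens, but that battery holds the two migraine outcomes and leaves out the measure that has an acceptability threshold. Someone who finds the app tedious or the relaxation unhelpful, and says so by withdrawing, is asked about migraine disability and quality of life but not about the app or the relaxation.

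If such people are less satisfied than those who remain, a mean taken over responders overstates satisfaction. The result could reach 4 when the mean over everyone assigned to the intervention would not. Willingness to repeat is exposed in the same way, although no pass mark hangs on it. Satisfaction scores not collected when people leave cannot be reliably recovered afterwards.

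**Working it through.** **Inputs from the plan.** Threshold: mean of at least 4 on a 0-5 scale (Aim 1). Dropout: 25% (sample-size text, Phase 2). Follow-through: about half (same text).

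**Inputs assumed.** The documents give no satisfaction scores. I take a responder mean R of 4.2 to 4.4 and vary the non-responder mean N. I use 50% missing only as an upper scenario, because follow-through is not defined as questionnaire response.

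**The plan's own figure.** 30 × (1 − 0.25) = 22.5, or about 23 per group, as stated. With a difference of 5.75, SD 7 and two-sided 0.05, 23 per group gives 79.5% power by the normal approximation (77.8% by the exact t calculation) against the stated 80%. That calculation concerns MIDAS change. The acceptability criterion has no sample size, power or confidence interval of its own, and only the 25% is carried forward.

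**Formulas.** With m the missing share:

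- overall mean = (1 − m) × R + m × N
- inflation of the observed mean = R − overall mean = m × (R − N)
- break-even non-responder mean = (4 − (1 − m) × R) / m

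**Inflation per point of gap (R − N = 1).** 0.25 at m = 0.25; 0.50 at m = 0.50.

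**Break-even values.**

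- m = 0.25, R = 4.2: (4 − 3.15) / 0.25 = 3.4
- m = 0.25, R = 4.4: (4 − 3.30) / 0.25 = 2.8
- m = 0.50, R = 4.2: (4 − 2.10) / 0.50 = 3.8
- m = 0.50, R = 4.4: (4 − 2.20) / 0.50 = 3.6

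**Overall mean if non-responders would average 3.0.**

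| Missing share | R = 4.2 | R = 4.4 |
|---|---|---|
| 25% | 3.15 + 0.75 = 3.90 | 3.30 + 0.75 = 4.05 |
| 50% | 2.10 + 1.50 = 3.60 | 2.20 + 1.50 = 3.70 |

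Three of these four cases cross the threshold; the case of 25% missing with R = 4.4 does not. If N equals R, the inflation is zero. If N is 4.0 and R is 4.4, the overall mean is 4.30 (25% missing) or 4.20 (50% missing), and the conclusion stands.

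**Which population.** Four of the nine items ask about the relaxation, and the PMR component is blocked in the version of the app given to MUC subjects. The nine-item mean can therefore apply only to RELAX. MUC subjects can answer only the five diary items.

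**The case against.** The strongest reply is that leavers are not ignored. Attrition is a named component of acceptability, and diary acceptability is examined through differential attrition. Reasons for non-adherence are a listed outcome, and focus groups draw on people who consented, not only on completers. This stands as far as it goes. But attrition has no threshold and does not enter the score, equal heavy loss in both arms would not show as a difference, and neither of the other two sources is stated to produce item scores from people who left.

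A reader might infer that the criterion is computed on completers only and is therefore biased upward. The documents do not support that. They give the items no time point, and the PROMIS, insomnia and stress questionnaires are named for REDCap administration without one either, so who would respond is unknown. That dislike causes leaving is plausible, but nothing in the plan shows it.

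A reader might also take "only about half of the participants have full follow-through" as a 50% response rate. It is not one. People without complete participation are still due contacts up to 6 months and are called if they do not complete the electronic assessment. The withdrawal request reaches only subjects who contact the team, and their number is not given, so the 25% and 50% figures describe total missingness and not the share this request would recover.

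Finally, counting non-response as dissatisfaction is debatable. Stopping the app is non-adherence by definition, whereas not answering a questionnaire is not evidence of dislike, and attrition is already reported separately. That rule belongs in a sensitivity analysis and not in the main result.

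**Conclusion.** The gap holds: the withdrawal request omits the items behind the only numerical acceptability criterion, together with the willingness item, and no other stated contact or missing-score rule fills it. The consequence is a risk of upward bias of 0.25 points per point of gap at 25% missing and 0.50 at 50% missing. Whether this changes the conclusion depends on three things the documents do not give: the responder mean, the non-responder mean and the actual missing share. Under the assumed responder means of 4.2 to 4.4, fairly modest gaps are enough, from 0.4 points (4.2 against 3.8, half missing) to 1.6 points (4.4 against 2.8, a quarter missing). The point affects a stated Aim 1 criterion and should be corrected. It does not bear on safety or on the migraine outcomes.

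**What to change.** Add the satisfaction items to the withdrawal request in Methods & Procedures, nine for RELAX and the five diary items for MUC, together with the willingness item. Collect the same items from everyone else at the 60-day contact (T3), which falls just after the 8-week intervention ends.

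State that the nine-item criterion of at least 4 applies to RELAX, with responses given at withdrawal included, and report how many scores are missing. Add a sensitivity analysis giving the proportion of all subjects randomised to RELAX whose own mean is at least 4, counting non-responders as not meeting it. The 6-month payment contact with withdrawn subjects can stay as it is: using it for research questions would mean revising an approved script and questioning people who have left, about four months after the intervention ended.

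The cost is a few short items on contacts that already exist, with no added visit. The reported score will probably be slightly lower. Subjects who stop responding without contacting the team remain outside the withdrawal request, and if they also miss T3 they are covered only by the sensitivity analysis.

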- 1. Please remember to use the app.
- 2. Hi, The RELAXaHEAD team is trying to reach you. Please call xxx-yyy-zzz [study phone number]?
- 3. You are due for your follow-up call/email. Please be sure to call us at xx-yyy-zzzz or respond to the email. The RELAXaHEAD team.

- 4. Remember-relaxation is beneficial for your health.
- 5. The best way to add relaxation into your routine is to pair it with an activity you do each day. Let us know if you want to discuss how to improve your adherence with the RELAXaHEAD app.
- 6. Research has suggested that the more one is able to practice relaxation, the better one's health. Log into the RELAXaHEAD app when able.
 - 7. We will text participants once a week from our NYU MCIT study phone confirming that we have recorded that they have spent x amount of time practicing PMR within the application, and asking if they have practiced PMR independently without the application that week.

Follow-up will be assured by testing the subject's phone number in front of the subject and asking for alternative contact information. Subjects will also be called/emailed.texted after 3 days of no daily diary entry. If they are not reached, an email via [contact] will also be sent as a reminder to input the data. During the calls, a designated study team member will reiterate the importance of adherence with the app. At 1,2 and 3 months, subjects will be asked to complete the MSQv2 and the MIDAS via phone or email to assess the treatment benefits. A designated study member will call the patient if they do not complete the assessment electronically. Throughout the study, subjects will be asked to record electronically any new and/or discontinued medications and interactions with the medical community. The study team also wants to collect additional patient information such as medications used before and after the research study (especially opioids), healthcare utilization, and comorbid diagnoses via i2b2, a member-driven non-profit foundation developing an open-source / open-data informatics community.

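### For subjects who formally withdraw before month 3 the plan describes no 3-month MSQv2 or MIDAS, and neither the exit-day score nor the 6-month contact can stand in for it

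*Combined protocol and SAP*

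**What the plan says.** The combined protocol and SAP deals with withdrawal in Methods & Procedures, just before the Symptoms Diary section. The rule applies "if any subject contacts us and want to withdraw from the study"; in that case, "we will ask them to complete the MSQv2 and MIDAS before they withdraw". The text then turns to later contact: "Subjects who withdrew will be contacted via telephone or email at the end of the 6 months study period", and the stated purpose is "in order to verify their email address to be used to send the reimbursement gift card for their study participation". No outcome questionnaire is attached to that contact.

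For subjects who have not asked to leave, the same section is more active. "At 1,2 and 3 months, subjects will be asked to complete the MSQv2 and the MIDAS via phone or email to assess the treatment benefits". If there is no electronic response, "A designated study member will call the patient if they do not complete the assessment electronically". Those who fall silent in the diary are pursued too: "Subjects will also be called/emailed.texted after 3 days of no daily diary entry".

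Table 2 (Aim 2) defines the MIDAS outcome as the "difference between scores of MIDAS" at 3 months and baseline. The Analysis Plan text names change in MSQv2 as the primary outcome and describes MIDAS as having a three-month recall. The only rule for dropouts, in the sample-size text, counts them as non-compliant. That settles the adherence outcome and says nothing about a missing MSQv2 or MIDAS.

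**The concern.** A subject who asks to withdraw before month 3 leaves two traces: questionnaires on the day of exit and an administrative contact at month 6. Neither is the 3-month measurement. The plan does not separate asking to stop the app and reminders from asking to leave outcome follow-up, so a person who only wants the first may be lost to the second.

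The loss may be related to arm. The diary and its reminders apply to both groups, but PMR practice exists only in RELAX, because that component is blocked in the MUC version of the app. Table 2 itself anticipates the time PMR takes and paradoxical anxiety as adverse events of PMR. If those who withdraw from RELAX tend to be those who benefit less, an analysis of the remaining subjects flatters RELAX. That would affect both the within-arm change hypothesised in Aim 2 and the between-arm difference used in the sample-size text.

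**Working it through.** **1. The plan's own figure.** Inputs from the sample-size text: SD of MIDAS change 7, difference 5.75, 30 per group less 25% dropout (30 × 0.75 = 22.5, about 23), two-sided 0.05, two-sample t-test.

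- Normal approximation: 5.75 / (7 × √(2/23)) − 1.96 = 2.786 − 1.960 = 0.826, which gives 79.5% power. The stated 80% reproduces.
- Exact t-test: 77.8%.

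The dropout allowance protects the number analysed. It does nothing about which subjects are missing.

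**2. Can the exit-day MIDAS stand in?** Take the recall window as 90 days. For an exit on day d before day 90, the days recalled from before enrolment number 90 − d.

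- Day 30: 90 − 30 = 60 of 90 days precede baseline.
- Day 60: 90 − 60 = 30 of 90 days precede baseline.

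Those days were already counted in the baseline score, so an early exit score largely repeats it. This argument is for MIDAS only, since the documents do not give the MSQv2 recall period. For MSQv2 the exit score is simply taken at a different time.

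**3. Can the 6-month contact stand in?** At about day 180 the recall window runs from day 90 to day 180. It shares no days with the 0 to 90 window of the endpoint.

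**4. Size of the bias.** Let m be the share of RELAX without a 3-month value through formal withdrawal, C the mean improvement of completers and W that of withdrawers. The mean for all is (1 − m)C + mW, so the completers' mean is too high by C − [(1 − m)C + mW] = m(C − W).

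The documents give neither m nor the gap C − W. Assumed ranges: m from 5% to 25%, where 25% is the plan's allowance for all dropout and so supposes that all of it is formal withdrawal; gap from 2 to 7 points, where 7 is one SD of MIDAS change.

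| m | gap 2 | gap 7 | gap 7 as share of 5.75 |
|---|---|---|---|
| 5% | 0.10 | 0.35 | 6% |
| 10% | 0.20 | 0.70 | 12% |
| 25% | 0.50 | 1.75 | 30% |

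These are errors in the RELAX mean. The between-arm difference is biased by m × gap in RELAX minus m × gap in MUC, so the figures carry over in full only if MUC has no such gap.

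**5. What the fix could recover.** Suppose a fraction a of withdrawers answer at day 90 and resemble the others. The remaining bias is m(1 − a) × gap × (1 − m)/(1 − m + am). For m = 25%, gap 7 and an assumed a = 50%: 0.125 × 7 × 0.75/0.875 = 0.75 points, down from 1.75.

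**The case against.** The strongest reply is that stopping PMR is not withdrawal. The risk section lets a subject stop the relaxation without any mention of leaving the study. PMR is used only as needed in weeks 6 to 8, the 90-day assessment falls after the 8-week intervention, and that assessment is paid separately from diary entry. All of this stands. A reader might infer that the 3-month outcome is never sought from anyone who stops. The documents do not support that: subjects who drop PMR or the diary but do not ask to leave remain in the 1-, 2- and 3-month assessments, with telephone pursuit.

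A reader might also infer that the contact already planned for withdrawers could deliver the endpoint. It could not, because it comes at month 6. A day-90 contact has to be kept for them.

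The follow-up schedule promises contacts at 3 months to all subjects, which could be read to include those who withdrew. The withdrawal paragraph gives them a separate path and does not say so; at best the text is ambiguous. Options for partial withdrawal may also appear in the consent form or the approved script, neither of which is available here. Contact after withdrawal depends on the subject's agreement in any case.

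Finally, this is a feasibility trial. Attrition is itself an outcome, Aim 2 looks for trends, and the sample-size text calls MIDAS change exploratory. That lowers the stakes, but it does not make an exit-day score a 3-month score.

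**Conclusion.** The point holds for subjects who formally ask to withdraw before the 90-day assessment, and only for them. The plan describes no 3-month MSQv2 or MIDAS for this group, and the two contacts it does describe cannot provide the Table 2 endpoint.

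The size is uncertain. Under the assumed ranges and a completers-only analysis, which the plan does not state, the RELAX mean is overstated by about 0.1 to 1.75 MIDAS points, against a target difference of 5.75. The upper end needs all of the planned 25% dropout to be formal withdrawal and a full SD between completers and withdrawers.

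A reader might be tempted to apply the remark that only about half have full follow-through, which with a 7-point gap would give 0.5 × 7 = 3.5 points. The documents do not support this: full follow-through is not defined, it is not equated with a missing 3-month score, and the share lost through formal withdrawal is not reported.

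This is a worthwhile, inexpensive improvement to a stated exit rule. It does not invalidate the trial.

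**What to change.** In the withdrawal paragraph of Methods & Procedures, separate stopping app use and reminders from leaving outcome follow-up. Offer anyone who asks to withdraw the choice to stop all app use and reminders but still receive the existing 90-day MSQv2 and MIDAS by email or phone, with the $25 already budgeted for the 3-month assessment under Payment for Participation. Record which choice was made. State that the exit-day score is kept as a descriptive record and is not used as the 3-month outcome.

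The cost is a short IRB amendment to the wording and script, and one retained day-90 contact for those who agree. No new instrument or visit is needed. Those who refuse are not contacted for outcomes, so some values will still be missing. The change has to be made before the subjects concerned pass day 90, since a 3-month score cannot be collected afterwards.

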The total N will be 490. We had an initial approval for N=402. Going forward, we are hoping to recruit an additional 90 subjects from the FGP Urgent Care Center and from the Neurology Urgent Care Center.

The initial stats were calculated as follows:

Sample size: Phase 1: 432 subjects, Phase 2: 90 subjects

Phase 1: The NCCIH uses the Kramer reference for power calculation. As indicated by Kraemer and colleagues, our pilot sample size (402) is based on the pragmatics of recruitment and the requisites for examining feasibility. We anticipate an adherence rate of at least 70%. If the adherence rate is below 50%, we will consider the approach in need of further refinement. Thirty patients per arm will allow estimation of an exact 95% confidence interval whose lower bound exceeds 50%. Therefore, insufficient adherence would be ruled out, assuming the true adherence rate is 70% or greater. This approach obviates the need to handle missing data, because subjects who drop out will be assumed non-compliant.

Thus, we plan to try to enroll migraine patients from the general neurology group, the NYU Headache specialists within the main academic center ([name]/ACC), the NYU Headache Center in the Men's Health Center and from [name] office. We would also like to recruit at MS Society events and other neurology events.

Research assistants will evaluate which patients are eligible to participate based on the inclusion and exclusion criteria stated below.

Phase 2: We arrived at the 90 urgent care subjects based on our initial power analysis and then the NIH's request in the Just in Time to increase the N up to 85.

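### Aim 2 in migraine patients has three incompatible primary outcomes (MSQv2 change, 3-month MIDAS change, or both), and the text wavers between a within-arm and a between-arm comparison

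*Combined protocol and SAP*

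**What the plan says.** All of these statements are current text in the combined protocol and SAP.

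**Primary outcome**
- Purpose of the Study, Aim 2, for migraine patients: "the primary outcome will be migraine quality of life and migraine disability measured by Migraine Quality of Life (MSQ) and the MIDAS". It gives no ranking and no rule for combining the two.
- Study Design, sample-size text, opening with "The initial stats were calculated as follows": "The planned sample size also provided adequate power for the primary exploratory outcome", which it identifies as the MIDAS change from baseline to 3 months.
- Analysis Plan: "Our primary outcome will be the change in the MSQv2". MIDAS follows as a further measure.
- Table 2, under the Aim 2 heading "MIGRAINE QUALITY OF LIFE AND MIGRAINE DISABILITY OUTCOMES": "Primary Outcome = Functionality", defined as the difference between the 3-month and baseline MIDAS scores. Despite that heading, the Aim 2 part lists no MSQ measure.

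The Pain Effects Scale (PES) is a further primary outcome for the MS-migraine group in the Aim 2 paragraph, and it sits beside MIDAS in Table 2. Study Design says that recruitment of patients with multiple sclerosis has closed. Post-traumatic headache patients are assigned only the secondary outcomes.

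**Comparison**
- Purpose of the Study, Aim 2: "Conduct within group analyses of the RELAX approach vs MUC", and then: "We hypothesize that at 3 months compared with baseline there will be trends in the RELAX arm towards decreased disability", measured by MIDAS.
- The sample-size text powers a difference between the groups with a two-sided two-sample t-test at 0.05.
- The Analysis Plan and Table 2 name no test or model for Aim 2.

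**The concern.** A primary label is useful only if it picks out one result before the data are seen. Here a report could present MSQv2, MIDAS or both as the primary result, and could rest on the change within the RELAX arm or on the difference from MUC, and each choice could cite some part of the text. If the scales disagree, or the within-arm and between-arm results disagree, the documents do not say which result goes forward to a larger trial.

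The comparison matters especially for MIDAS. Migraine patients must score above 5 on MIDAS to enter, and the same scale is then re-measured. Patients selected for high scores tend to score lower later whatever they receive, so improvement within the RELAX arm cannot separate an effect of relaxation from regression to the mean. The MUC arm is there to make that separation.

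**Working it through.** **1. Which outcome is primary**

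| Place | Primary outcome | Time point given there |
|---|---|---|
| Purpose of the Study, Aim 2 | MSQ and MIDAS | 3 months, in the hypothesis, for MIDAS |
| Sample-size text | MIDAS change | 3 months |
| Analysis Plan | MSQv2 change | none |
| Table 2 | MIDAS change (PES beside it) | 3 months |

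Methods & Procedures collects both scales at 1, 2 and 3 months, so the Analysis Plan sentence leaves three candidate times for MSQv2.

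**2. The plan's own power figure**

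Inputs from the sample-size text: difference 5.75, SD 7, 30 per group, 25% dropout, two-sided 0.05.
- Completers: 30 × 0.75 = 22.5, about 23 per group.
- Standardised effect: 5.75/7 = 0.82.
- Standard error of the difference: 7 × √(2/23) = 2.064. Ratio: 5.75/2.064 = 2.786.
- Normal approximation: Φ(2.786 − 1.960) = 79.5%.
- Exact noncentral t, 44 df: 77.8%.

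The stated 80% is reproduced by the normal approximation. It belongs to one scale (MIDAS) and one comparison (between arms).

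**3. The same inputs read within one arm (illustration)**

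- Standard error of a mean change: 7/√23 = 1.460. Ratio: 5.75/1.460 = 3.939.
- Exact one-sample t, 22 df: 96.4%.

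So 5.75 points is detected with 96.4% power as a change within one arm and 77.8% as a difference between arms. These are different quantities, and only the second is a treatment effect.

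A further illustration assumes no true difference between arms and an equal improvement in both of 2, 3 or 4 MIDAS points (SD 7, 23 per arm). A within-arm t-test at 0.05 would then be significant in 26%, 50% or 75% of trials, against 5% for the between-arm test. The documents give no expected MUC change, so these shifts are assumptions.

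**4. Completers under the current 90 patients**

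Equal allocation is assumed: 90/2 = 45 per arm.
- About half follow through, as the sample-size text reports: 45 × 0.5 = 22.5, so 22 to 23 per arm.
- 25% dropout: 45 × 0.75 = 33.75, about 34 per arm.
- All complete: 45 per arm.

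Full follow-through is not defined and may not mean having a 3-month score, so the whole range is shown.

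**5. MSQv2**

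The documents give no SD or target difference, so its power cannot be computed. At assumed effects of 0.3, 0.5 and 0.8 SD, exact-t power would be 17%, 38% and 76% with 23 per arm; 23%, 53% and 90% with 34; and 29%, 65% and 96% with 45. These only show that the MIDAS figure cannot be carried over to MSQv2.

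**The case against.** The best defence is that the text already points to MIDAS. The Analysis Plan opens by referring the reader to Table 2 for the outcome measures, Table 2 labels MIDAS change as primary, the sample-size text agrees, and the only Aim 2 hypothesis for migraine patients is on MIDAS. On this view one MSQv2 sentence is the outlier. That stands as a reason to choose MIDAS. It does not settle the matter, because the Aim 2 paragraph names both scales and no statement gives Table 2 precedence.

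A second defence is that Aim 2 is exploratory and the trial is sized on adherence to relaxation. This also stands, and it limits the consequence. A reader might infer that the missing MSQv2 power calculation makes the trial inadequate. The documents do not support that: an exploratory outcome in a trial sized on feasibility needs no power calculation. Nor do they support the inference that the MIDAS power is wrong, since it reproduces.

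Third, no within-arm significance test is specified anywhere. Aim 2 speaks of trends, and its within-group sentence itself ends with a reference to MUC. A reader might infer that the plan commits to judging the treatment by a within-arm p-value. It does not, so the within-arm figures above are illustrations only. What remains is wording that allows either comparison.

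Finally, the conflict might be taken as evidence that the outcome was switched after results were seen. Nothing in the documents shows that.

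**Conclusion.** The point holds as a contradiction in current text. For migraine patients, Aim 2 has three incompatible primary designations and an unclear comparison, and no rule resolves either. The text leans to MIDAS at 3 months. The severity is moderate: the plan should be corrected because it leaves room for selective reporting, but the feasibility aim and the stated MIDAS power are unaffected.

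The contradiction itself rests on no outside assumption. The contrast of 96.4% with 77.8% uses the plan's own inputs at 23 completers per arm. That number is uncertain under the current 90 patients, plausibly 22 to 45 per arm with equal allocation.

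**What to change.** By dated amendment, reconcile the Aim 2 paragraph, the sample-size text, the Analysis Plan and Table 2:

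1. Name one Aim 2 primary outcome for migraine patients at 3 months, analysed as the RELAX-minus-MUC difference in change from baseline. MIDAS change fits Table 2, the hypothesis and the power text.
2. Report within-arm change as descriptive only.
3. List MSQv2 in Table 2 as secondary, and state that PES applies only to the closed MS-migraine group.
4. If MSQv2 is chosen instead, state 3 months as its time point, add it to Table 2, and do not cite the MIDAS power for it.
5. If both scales stay primary, state the success rule or label Aim 2 as estimation only.
6. State whether outcome data by arm had been seen when the choice was made, and report both scales in any case.

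The cost is one amendment with IRB review, with no new data or visits. The downside is that one scale loses primary status, and the disclosure may show that the choice was not made blind.
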